3. Identify what additional COVID-19 information district and school leadership would like to help address concerns about in-person school participation
4. To understand the facilitators and barriers to testing, attending in-person school, and vaccination
5. To understand the social, behavioral, and ethical factors driving decision-making about in-person school participation.

1.4.22 The pre-message interviews and focus groups have been completed as outlined above. The first round of messages have been developed to increase communications within the schools. This is targeted at increasing participation in testing.

B. Timepoint 2

Recruitment and Consent

Enrollment/Consent Process: Focus Groups / Listening Sessions:

The participating school districts will share project description through multiple methods (e.g., email, social media, electronic platforms, meetings) with students, parents/caregivers and school staff. One of the methods will be to share a listening session recruitment flyer. [attachment:01 Recruitment Flyer Mar22] Evaluation Center and community partners will share a recruitment flyer through multiple methods (e.g., email, social media, PeachJar, meetings) and will also recruit participants via phone call [attachment: 02 Recruitment Phone Script Mar22].

Individuals interested in participating in discussion sessions will contact the research team to enroll or complete the Qualtrics survey displayed in recruitment flyer. [attachment: 03 LSSignupSurvey Mar2021].

Within approximately 1-2 business days after initial contact the research team will follow-up with a confirmation email, including a project overview flyer, consent documents based on age group, and a link to a demographics survey [attachments: 04 LSConfirmationEmail Mar22, 05 DemographicsSurvey Mar22, 06 ConsentForms Students Mar22, 07 ConsentForms TeachersParents Mar22, 08 ProjectOverview Mar22]. Please note: the Project Overview includes a QR code, which directs interested participants to a schedule of available COVID-19 testing [attachment: 09 QRLandingPage Mar22]. Reminders will be sent one day and one hour prior to the listening session date via email, text message and/or phone call [attachment: 10 SessionReminder Mar22].

Participants who are 18 years and over that attend listening sessions will provide verbal consent at the beginning of the session. Research team members will obtain parent/guardian consent for student participants who are under 18 years old prior to the session.

Discussion sessions will be conducted virtually (via Zoom), over a phone call, or in person with approximately 1-15 participants. Sessions will be led by at least one facilitator and at least one note taker. Facilitators will use a guide to assist with facilitating the discussion session. All sessions will be recorded and subsequently transcribed. See below for listening session objectives and topics to be covered.

Enrollment/Consent Process - Qualitative Overview: Administrator Interviews

The Evaluation Center will host listening sessions with both district-level leadership (superintendents and assistant superintendents), as well as school-level leadership (principals and assistant principals). The Evaluation Center project team members will share project description and recruitment of school administrators via email [Attachments:03 Admin Recruitment Email; 04 Principals Recruitment Email].

District-level individuals interested in participating in a discussion will complete a Doodle poll to identify a time that works for the group. School-level individuals interested in participating in a discussion will fill out the signup link provided via a recruitment email sent by the Evaluation Center team [Attachment: 05 Principal Qualtrics]. Within approximately 3 business days of contacting research team, interested individuals will be emailed a confirmation of their schedule interview time, along with the following: Emailed consent cover page [attachment: 01 Listening Session Cover Page] and emailed consent information sheet [attachment: 02 Listening Session Consent Form]. They might receive a phone call or text confirmation of the interview time as well.

Reminders will be sent 1 day prior to the interview via email, text message, and/or phone by a member of the Evaluation Center team. Interview participants will provide verbal consent at the beginning of the session. Interviews will be conducted virtually via Zoom or phone depending on interviewee preference. Interviews will be led by one facilitator and one note taker.

Listening Session Questions and Objectives

These interviews and group sessions will occur amongst students, staff, and household members in all five school districts identified for the project. The overall purpose is to understand if frequent screening testing will provide additional benefit, beyond current school-based mitigation strategies, to prevent SARS-CoV-2 transmission in schools. Individuals will be asked to give their insight to understand the social, behavioral, and ethical factors driving testing and in-person school participation. They will also be asked about experiences returning to school and during COVID. The research team will also ask about the facilitators and barriers to SARS-CoV-2 testing, attending in-person school, and vaccination. The sessions will be recorded and the recordings will be transcribed.

Listening Session Objectives

1. Understand the perceived risks of COVID-19 for staff and students while being at school since T1.
2. Understand what role, if any, testing and vaccination plays in mitigating perceived risk.
3. Identify information and resources that are needed to keep students and staff in school.
4. Understand the social, behavioral, and ethical facilitators and barriers to testing, attending in-person school, and vaccination in the school community.

C. Empowerment (CDE) listening sessions:

Sessions will be conducted with school parents/caregivers and school staff, community partner staff, and residents of St. Louis City and St. Louis County. These sessions will occur either on zoom or in person. Individuals will be asked questions about the common data elements in a semi-structured interview fashion. They will be asked questions about their thoughts on the CDEs, which questions they would like asked, and how the team can be better informed regarding the data collection process and resulting information. Individuals will read a consent information sheet prior to participating. These sessions will be audio-recorded for transcription and data analysis. Prior to the sessions participants will be sent a brief demographic form to complete.

D. Implementation Evaluation

Anyone who has participated in either/both forms of testing, as well as individuals in the school who did not participate in the study, will be asked to complete a survey and participate in a focus group evaluating the study implementation. The surveys will be distributed over REDCap with a consent information sheet to read before completing. Following completion of the survey participants will be contacted by phone to schedule participation in a focus group or interview. A phone, text, or email reminder will be sent for focus groups and interviews in advance of the scheduled time. Individuals will read a consent information sheet prior to participating in the focus groups, which will occur over zoom or in person. These sessions will be audio-recorded for transcription and data analysis.

Individuals who aided in the implementation of the testing protocol, such as research team members or community partners, will be asked to participate in a discussion session. A phone, text, or email reminder will be sent for focus groups and interviews in advance of the scheduled time. Individuals in this group will not be asked to complete a survey prior to the discussion session. Participants that attend discussion sessions will review a consent information sheet at the beginning of the session

before participating. They will be given time to review the information and ask questions. Discussion sessions will be conducted virtually (via Zoom) or in person. These sessions will be audio-recorded for transcription and data analysis.

E Statistical Plan

Power calculation: A cluster randomized trial (CRT) will be conducted at 12 schools that provide symptomatic SARS-CoV-2 testing to students and staff. Schools will be randomized 1:1 to either screening testing plus symptomatic testing, or symptomatic testing only. All participants including students and staff will receive the same assignment within a given school. The primary outcome is transmission rate, defined as the ratio of the number of contacts testing positive for SARS-CoV-2 to total number of contacts for each school-based case. We hypothesize that schools performing screening testing will have lower transmission rates than routine symptomatic testing. We expect that transmission rates with screening testing or routine symptomatic testing will be 2% and 8%, respectively. With the assumptions that the intracluster correlation coefficient (ICC) is 0.02 and the standard deviation of transmission rate is 0.22, 6 schools in each arm with an average of 117 participants per school will achieve 80% power to detect a difference in transmission rates between the two study arms using a two-sided t-test at a significance level of 0.05 (Table 3). PASS 15.0 was used to conduct this power analysis.

Table 3. Sample Size

| ICC | Standard deviation | # of participant per school |
|------|--------------------|-----------------------------|
| 0.01 | 0.25 | 83 |
| | 0.30 | 188 |
| | 0.33 | 376 |
| | 0.35 | 803 |
| 0.02 | 0.22 | 117 |
| | 0.23 | 164 |
| | 0.24 | 252 |
| | 0.25 | 486 |
| 0.03 | 0.20 | 221 |
| | 0.21 | 806 |

Analysis plan: The generalized estimating equation (GEE) model with appropriate link function (e.g., identity for primary outcome) will be used to analyze the CRT data, in which the correlation among participants within each school needs to be considered. The autoregressive of first order as a working correlation structure will be used, and participants with missing values will be excluded from the GEE analysis. The GEE model includes the group indicator and other potential factors, including: race/ethnicity, insurance status, age, gender, underlying diagnoses, masking, distancing, ventilation, location of transmission. Least square means for the primary outcome per group will be estimated, and the standard errors will be calculated with the GEE sandwich method when accounting for within-school correlation. All analyses will be conducted using SAS (SAS Institute, Cary, NC) at the two-sided significance level of 0.05.

Data Management.

All testing data are maintained in a secure, password-protected REDCap database. Information collected on paper forms is stored in locked filing cabinets on a restricted-access floor at WUSM. Prior to undergoing testing, participants will complete a HIPAA authorization form and/or informed consent to allow SARS-CoV-2 testing data to be shared with the State of Missouri. All participants are assigned an ID number, and testing information is kept separate from the demographic data. Subjects who test positive are contacted by phone to

be given their results. This information will be shared only with the participant unless an informed consent is signed that will allow sharing of their data with the RADx-UP Coordination and Data Collection Center. For students and staff who complete informed consent, their positive results will be shared with the relevant school, after the individual has been notified and provides verbal re-confirmation of their permission to share that information.

Data are stored using HIPAA-compliant encryption to comply with all local, state, and national regulations for health-related data. Consent will be obtained from participants for future use of biospecimens (saliva), and these biospecimens will be stored in a -80°C freezer. The consent form will allow participants to opt-out of having their saliva specimens stored and being contacted for future research studies including COVID-19 vaccination trials in children.

Our existing Consortium Data Reporting Unit (CDRU), in collaboration with our data manager, will coordinate the submission of common evaluation metrics on SARS-CoV-2 testing-related outcomes to the RADx-UP CDCC at Duke University. We will comply with data sharing as mandated by the NIH and follow guidance provided by the CDCC for data acquisition, collection, and curation, including appropriate consent for data sharing and implementation of the schemas proposed under the ABOUT ML effort. The CDRU will also ensure compliance with federal, state, and local requirements and policies for testing, reporting, and surveillance. The CDRU will also work closely with the CDCC to employ a common set of tools to promote collection of comparable data on social determinants of health, including measures from the PhenX Toolkit. Effective implementation strategies for rapid adoption will be disseminated through the CDCC.

We will work collaboratively with the Duke CDCC in reviewing and revising our data collection tools to ensure we are collecting the appropriate CDEs. We will share our data with Duke CDCC. Finally, we will share our findings with the participating school districts and community partners at regular intervals throughout the project.

Publicly Available Information. We will make the aggregate results of the surveys, discussion sessions, and testing results publicly available on the following website: <https://safereturntoschoolstudy.wustl.edu/>. Additionally, we will provide a flyer at the end of the study to participants sharing aggregate results, provide study updates, and include relevant information regarding the pandemic.

F Study Monitoring

Study Monitoring Plan

A plan is in place to monitor for emerging differences in school based-transmission between the two testing strategies. Quarterly, [name] (PI), [name] (Co-I), and two independent monitors, Drs. [name] (Division Chief of Pediatric Infectious Diseases) and [name] (Pediatric Infectious Diseases physician and virologist), and the trial statistician, [name], will review the data. Drs. [name] and [name] will monitor the volume of SARS-CoV-2 tests being obtained at the schools, rates of SARS-CoV-2 positivity in all schools, and the number of potential transmission events within the schools on a continuous basis.

Important to this study is the monitoring of the social, ethical, and equity implications associated with the testing implementation in these underserved communities. All participants will be given the opportunity to express their concerns and identify barriers to participating in the study at time of enrollment. Additionally, a study email and phone number will be available for participants to provide feedback and voice any concerns about the project.

G References

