Follow-up Protocols: Testing results will be available within 24 to 72 hours. All students, staff, and household members with positive results will be notified by [name] and/or a member of the study team and information regarding appropriate isolation and quarantining for contacts will be provided to comply with prevailing National/County health department recommendations. Additional financial and social services needed for the student and family due to isolation and/or quarantine procedures may be coordinated with the school and community partners. Finally, all positive individuals may have a 3-week phone call follow-up to inquire about the outcome of their illness including the need to seek medical attention and/or be hospitalized. For those in the contact arm, there might be additional questions if the

individual tests positive related to: activities, behaviors, and potential school based exposures.

Assessment of School Mitigation Strategies: Ascertaining the mitigation practices in place for each school is essential for evaluating the impact of additional testing on school transmission. A school-based mitigation strategy survey (Appendix 1), developed in conjunction with the CDC and utilized in prior school-based investigations, may be completed by each school at the beginning of the project. Questions in this survey will include: method of instruction (e.g., hybrid, type of hybrid, fully in-person) and date implemented, masking recommendations and perceived compliance, distancing in classrooms, use of physical barriers (e.g., Plexiglas), location and processes for eating lunch, and mitigation strategies used in extracurricular activities (e.g., sports, choir, band). Schools will also be asked about their quarantine rates and new school based cases/contacts on a weekly basis. This will help understand the rates of transmission in the schools.

Assessment of School-based Transmission: The primary outcome for this study will be the average of the secondary attack rate of school-based transmission per case at each school. For example, if a case has 10 contacts and 2 become infected, the secondary attack rate for that case would be 20%.

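### The primary outcome is one attack rate per index case, but power and the GEE count undefined participants and no index-case number is projected, so the 80% power is not shown for that outcome

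*Combined protocol and SAP*

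**What the plan says.** Section D1 (Assessment of School-based Transmission) states: "The primary outcome for this study will be the average of the secondary attack rate of school-based transmission per case at each school". Its example gives one value for one case: 2 infected among 10 contacts is 20%. Section E (Power calculation) agrees. The transmission rate is "defined as the ratio of the number of contacts testing positive for SARS-CoV-2 to total number of contacts for each school-based case".

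The counted unit then changes. The same paragraph says that "6 schools in each arm with an average of 117 participants per school will achieve 80% power", assuming an ICC of 0.02 and that "the standard deviation of transmission rate is 0.22". Table 3 is also in participants per school. The paragraph's only description of participants is that they include students and staff. The Analysis plan uses a GEE with identity link in which "the correlation among participants within each school needs to be considered". It adds "The autoregressive of first order as a working correlation structure will be used", and "the standard errors will be calculated with the GEE sandwich method when accounting for within-school correlation". The candidate covariates are "race/ethnicity, insurance status, age, gender, underlying diagnoses, masking, distancing, ventilation, location of transmission".

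The planned volumes in section C (Description of milestones and timeline completion) are tests: about 3,000, 5,000, 8,000 and 10,000 in the four quarters of year 1. No count of index cases, contacts per case or positivity rate is projected. New cases and contacts are to be collected from the schools every week.

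The number of schools also differs. It is 12 in sections A and E, but 16, with 8 randomized to screening, in section C (Study Setting and Populations) and section D1 (Screening Testing).

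**The concern.** If the outcome is one ratio per index case, the sample size that drives power is the number of index cases per school. That number depends on the epidemic, not on enrolment. A school can have several hundred consented people and few cases. A power statement in participants cannot be checked against expected accrual, and it gives no warning if cases are scarce.

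The undefined row also leaves the analysis open. Rows could be index cases, contacts or school means, and these weight the data differently. First-order autoregression makes the fit depend on the order of rows within a school, and the plan names no order. The covariate list does not settle the matter. Age or insurance could describe a case or a contact, while section D1 records distance, masking and location for each case-contact pair. With 12 schools, an uncorrected sandwich standard error also tends to be too small.

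**Working it through.** **Inputs (section E).** Rates 2% and 8%, difference 0.06; SD 0.22; ICC 0.02; 6 schools per arm; 117 per school; two-sided 0.05.

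**1. The plan's own figure.** With k schools per arm and m rows per school:

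- Design effect: 1 + (117 − 1) × 0.02 = 3.32.
- Effective rows per arm: 6 × 117 / 3.32 = 211.4.
- Noncentrality: 0.06 / (0.22 × √(2/211.4)) = 2.80.
- Power from the noncentral t on 2km − 2 = 1,402 df: 80.0%.

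Table 3's ten rows reproduce in the same way, all at about 80%. The arithmetic is correct with participant-level df.

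**2. The same inputs with index cases as rows.** If m is the number of index cases per school, SD and ICC unchanged:

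| Index cases per school | 6 per arm, participant df | 6 per arm, 10 df | 8 per arm, participant df | 8 per arm, 14 df |
|---|---|---|---|---|
| 10 | 28% | 24% | 35% | 32% |
| 30 | 54% | 46% | 66% | 60% |
| 50 | 66% | 57% | 78% | 72% |
| 117 | 80.0% | 71.5% | 90% | 85% |

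With 12 schools, 117 per school is 12 × 117 = 1,404 index cases. To reach 80% on school-level df takes 320 per school with 6 per arm, or 77 with 8 per arm. On participant df it takes 117 or 55.

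**3. Why the direction is unknown.** A quantity between 0 and 1 has its largest SD when it is all-or-none: √(0.02 × 0.98) = 0.140 and √(0.08 × 0.92) = 0.271. Pooled, this is √((0.0196 + 0.0736)/2) = √0.0466 = 0.216. The stated 0.22 is therefore about the maximum for a per-case ratio at these rates, and a ratio over several contacts would normally vary less. With 10 index cases per school, 6 schools per arm and ICC 0.02:

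| Per-case SD | Participant df | 10 df |
|---|---|---|
| 0.07 | 99% | 97% |
| 0.10 | 85% | 78% |
| 0.15 | 52% | 45% |
| 0.22 | 28% | 24% |

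The documents give no per-case SD. As an illustration, assume n = 2 to 10 contacts per case and a within-case correlation ρ of 0.02 to 0.30. Then SD = √(0.0466 × (1 + (n − 1)ρ)/n) runs from 0.07 to 0.17. With ICC 0.02 on the per-case scale and 6 schools per arm, 80% power needs 5 to 39 index cases per school on participant df, or 6 to 59 on 10 df.

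**4. Sandwich standard error with few schools.** Take equal-sized schools, a model with group only, no small-sample correction and a normal reference. With 12 schools the type I error is P(|t₁₀| > 1.96 × √(5/6)) = 0.104. With 16 schools it is P(|t₁₄| > 1.96 × √(7/8)) = 0.088.

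**5. Numerator and denominator.** Section E divides positive contacts by all contacts of a case. In section D1 the first method has positive contacts reviewed and classified as to whether transmission was school-based. The second method divides positive contacts by positive cases, which is a different denominator.

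**The case against.** The strongest reply is that the unit is less obscure than it looks. The definition in section E, the worked example in section D1, the identity link, the t-test and the SD of a rate all suit one continuous value per index case. On that reading 0.22 is close to a worst-case SD, so the calculation is conservative in that input. Cases and contacts are collected weekly, and section F has positivity and potential transmission events monitored continuously. Accrual would therefore be seen, even though it is not forecast. With 16 schools, 117 rows give 90%, or 85% on school-level df. All of this stands. What it does not supply is a statement that the 117 are index cases, or any ground for expecting that many.

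Some stronger readings are tempting, and the documents do not support them:

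- **The trial is underpowered.** Lower power follows only if SD 0.22 holds and index cases are few. Neither is established.
- **The sample size is miscalculated.** It reproduces.
- **SD 0.22 proves that the calculation was made for contacts.** Table 3 runs from 0.20 to 0.35, and its three rows at 0.30 to 0.35 exceed the all-or-none maximum in either arm (0.271). The grid does not look derived from a yes/no outcome.
- **Case, contact and school-mean rows must give different answers.** They diverge in expectation only if the attack rate varies with contacts per case or cases per school, and the documents are silent on both.
- **The planned test has 10% type I error.** The plan adds covariates and names no reference distribution, so that figure is indicative only.

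**Conclusion.** The point holds as not shown. The 80% is correct arithmetic for 117 rows per school with participant-level df. The plan neither identifies those rows with the index cases on which the outcome is defined nor projects how many index cases there will be. At the stated SD and ICC with 12 schools, the claim requires 1,404 index cases. Power is 28% to 66% for 10 to 50 per school, on the plan's own choice of df. A smaller per-case SD could offset this entirely, so no single corrected figure can be given.

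Two further results do not depend on the case count. If all 117 rows per school are obtained, moving to school-level df takes power from 80.0% to 71.5% with 6 schools per arm, or from 90% to 85% with 8, so the number of schools must be settled first. The autoregressive structure on rows with no stated order and the uncorrected sandwich with 12 or 16 clusters have better and inexpensive alternatives.

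**What to change.** 1. Reconcile 12 and 16 schools throughout the protocol.
2. In sections D1 and E, state that one row of the primary analysis is one index case, clustered by school. Say how pair-level covariates (distance, masking, location) are summarised per case, or drop them from the primary model.
3. Use one numerator (any positive contact, or positives judged school-based) and one denominator throughout, and label the second method's positives-per-case ratio as a separate measure. State how index cases with no contacts are handled, since their ratio is undefined.
4. Replace the autoregressive structure with working independence. Use a small-sample-corrected sandwich with a t reference on school-level df.
5. Replace participants per school with projected index cases per school and contacts per case. Restate power for the reconciled number of schools over a range of per-case SD and ICC, on school-level df.

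The cost is protocol wording and a recomputed Table 3, with no change to study procedures. The restated power may be less favourable than 80%.
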